# Severity

The Investigator will use the following definitions of severity in the evaluation of AEs:

- Mild: An AE that is easily tolerated and does not interfere with daily activities.
- Moderate: An AE that is sufficiently discomforting so as to interfere with daily activities.
- Severe: An AE that prevents normal everyday activity.

Note that "severe" is not synonymous with "serious": an AE may be assessed as severe without meeting the criteria for an SAE (see above)

### **Assessment of Relationship to Study Drug**

The following definitions of relationship should be used to characterize the suspected causality of each AE as either related or not related to pre-rolled TachoSil®. This assessment should be based on the Investigator's consideration of all available information about the event, including temporal relationship to drug administration, recognized association with drug product/class, pharmacological plausibility, and alternative etiology (e.g., underlying illness, concurrent conditions, concomitant treatments):

- Related: There is a reasonable possibility that the drug caused the event.
- Not related: There is not a reasonable possibility that the drug caused the event

#### **Adverse Reactions**

For the purposes of this study, an adverse reaction is an AE that is considered related to pre-rolled TachoSil® according to the definition above.

#### **Outcome**

• **Fatal:** The patient died due to the event. If the patient died due to other circumstances than the event the outcome should be stated as 'Not recovered' or 'Recovering'.

- Recovered/Resolved: The patient has fully recovered from the event or the condition
  has returned to the level observed at baseline.
- Recovering/Resolving: The event is improving but the patient is still not fully recovered.
- Not Recovered/Not Resolved: The event is ongoing at the time of reporting and the
  patient has still not recovered.
- Recovered with Sequelae/Resolved with Sequelae: As a result of the event, the
  patient suffered persistent and significant disability/incapacity (e.g. became blind, deaf
  or paralysed).
- Unknown: If Outcome is not known or not reported.

## 9.3 Reporting of Adverse Events

Documentation of AEs will commence after a patient has provided informed consent and pre-rolled TachoSil® was applied in that patient. AEs and SAEs (which include all deaths) must be reported, whether or not considered causally related to pre-rolled TachoSil®.

In case of a SAE, the Investigator will notify the Sponsor through use of the SAE form, within 24 hours after the Investigator becomes aware of the event. The event must be documented in source documentation.

AEs which do not meet the criteria of SAEs are documented through use of the AE form within the study CRF.

After receipt of the initial report, the information will be reviewed, and the Investigator might be contacted to request additional information or for data clarification. If required, a follow-up report, including all new information obtained on the event, must be prepared and sent to the designated contact of the Sponsor.

The Sponsor assumes responsibility for reporting of AEs/SAEs occurring in patients exposed to pre-rolled TachoSil® to regulatory authorities according to legal requirements.

## 9.3.1 Reporting of Pregnancy and Breast-feeding

Any case in which a pregnant patient or a patient that is breast-feeding is exposed to prerolled TachoSil® this information needs to be forwarded to the Sponsor using the SAE form regardless whether an AE results or not.

### 9.3.2 Reporting of Medication Error

All information of medicinal product medication error, suspected transmission of an infectious agent or lack of effect relating to pre-rolled TachoSil® regardless of whether an SAE results or not, need to be forwared to the Sponsor using the SAE form.

# 10 Data Quality Control and Assurance

# **10.1 Quality Control**

The quality of data and adherence to the NIS protocol, to legal and ethical requirements will be overseen by the CRO applying a combination of centralized and on-site monitoring.

All CRFs will be reviewed for pre-defined criteria (e.g. ICF, AEs and study treatment), and queries will be raised in case of deviations.

On-site visits will be scheduled in approx. 5% of sites (1 Austrian and 3 German sites), including source data verification of pre-defined items (e.g. ICF, AE data and Patient Identification List).

The extent and nature of quality assurance will be described in detail in the monitoring plan. If applicable, for further information see sponsor SOPs: G-SOP-MA-005, C-GUID-DO-354 and C-GUID-DO-333.

### 10.2 Audit from Quality Assurance Unit

The Quality Assurance (QA) unit may audit the study to ensure that study procedures comply with the protocol and standard operating procedures, and that collected data is correct and complete.

### 10.3 Inspection by IEC or Competent Authority

Representatives from EC or Competent Authority may in rare cases wish to inspect the study on site. Upon receiving notification of such inspection, the Study Site Responsible must immediately contact the Sponsor and must make the records available as requested.

### **10.4 Data Management**

The CRO is responsible for Data Management carried out according to a Data Management Plan. A data management plan, which will include the description of plausibility checks, will be prepared before the start of data entry.

If the written informed consent of a patient is known not to be available in spite of it being required, data for this patient is not entered into or is deleted from the database.

If a patient is erroneously included in the study more than once only the data relating to the first inclusion will be kept in the database and be available for analysis.

If a patient is included in the study in spite of being treated off-label (not according to the SmPC), data is kept in the database and analysed as described in the Statistical Analysis Plan.

The current Standard Coding Instructions for coding of medical history, concomitant illness (MedDRA), concomitant medication (WHO-Drug) and adverse events (MedDRA) must be followed.

The patients will be identified in the database only by Study ID, Site ID, patient number, year of birth, and gender.

### 10.4.1 Data Collection Tools and Flow

The Study Site will receive data collection tools (Case Report Forms (CRFs)) from CCI.

Whenever possible, complete data sets should be entered. Text field entries and any data collected on paper should be legible and follow the requested language standard.

The Study Site Responsible must sign off the complete data set for each patient, confirming the collected data. SAE data collected and reported according to section 9.3 should be signed off separately by a physician who may or may not be involved in the study.

The Study Site will provide completed CRFs directly to the responsible CRO syneed medidata.

### 10.4.2 Query management

In case of incomplete or inconsistent entries regarding predefined CRF-items (e.g. informed consent, study treatment) the CRO will contact the respective physician in writing for clarification or completion of missing data.

In case of incomplete or inconsistent entries regarding AEs or SAEs, the Sponsor will contact the respective physician for clarification. Prior to database lock, a reconciliation of study-related safety information with the sponsor's safety database will be performed.

# 11 Statistical Methods and Determination of Sample Size

In general, summary statistics (mean, median, standard deviation, minimum, and maximum) will be provided for continuous variables, and the number and percentage of each category will be provided for categorical data. Any changes in the original statistical methodology will be documented in the statistical analysis plan (SAP), a separate document provided by the CRO

# 11.1 Statistical Analysis Plan

This study is observational and epidemiological methods will be employed for data analyses. All statistical details including calculated variables and proposed format and content of tables will be detailed in the SAP, a separate document provided by the CRO

The SAP will be finalized before study database lock. The analysis will be performed in accordance with the European Network of Centres for Pharmacoepidemiology and Pharmacovigilance (ENCePP) Guide on Methodological Standards in Pharmacoepidemiology [R5].

Statistical analyses will be performed using validated statistical software (e.g. SAS®, SAS Institute Inc.).

Descriptive analysis will be performed of all collected data except data collected only for the purpose of data cleaning. All AEs will be listed as described in the SAP in section 5.

The main outcomes of the study are:

#### Primary

Assessment by the surgeon with respect to ease of use and overall satisfaction in the operation, using 5-Point-Likert-Scales (1 = easy/satisfied, 5 = difficult/ not satisfied)

[Time Frame: intra- and post-surgery until hospital discharge]

#### Secondary

- Length of hospital stay (ICU and normal hospital station)
   [Time Frame: Date of surgery until hospital discharge]
- Pharmaco-economic evaluation as assessed by the surgeon [Time Frame: intra- and post-surgery until hospital discharge]
- Safety intra- and post-operative adverse events
   [Time Frame: from study start to study end]

# Health economics

Cost analysis (length of hospital/ICU stay, avoidance of complications, cost savings) based on information given by physicians and pecuniary considerations (cost per minute of surgery/day in ICU/day in normal ward)

AEs/SAEs reported in the study as well as AEs/SAEs reported directly to authorities and to Takeda Drug Safety according to section 9.3 and not captured in the study database will be extracted from the overall safety database and the study database and listed or tabulated in the final report in the standard way of presenting such data in a Periodic Safety Update Report (PSUR).

# 11.2 Interim Analyses

No interim analyses are planned for this study.

# 11.3 Determination of Sample Size

It is planned to collect data from up to 50 german hospitals and 10 ustrian hospitals performing laparoscopic surgery, from departments of gynecology, urology and visceral surgery. Each study centre should document only up to 20 patients.

As primary outcome measures the peri- and post-surgery assessment by the surgeon with respect to ease of use and overall satisfaction in the operation, using 5-point-Likert-Scales (1 = easy/satisfied, 5 = difficult/ not satisfied) are fixed in the study protocol. It is expected that

the use of pre-rolled TachoSil® is easier than the application of planar TachoSil® prepared/rolled by the surgeons themselves.

No published paper could be found with an identical outcome measure 'ease of use', which could have served as base for sample size calculation. Therefore the results of an older study with a specific MIS -applicator as a surrogate approach (Nycomed Arzneimittel GmbH 1998) were used.

Amongst others a parameter called 'Handhabungs-Score' (handling- score) was considered as outcome parameter according to the study protocol. This parameter comes very close to the parameter 'ease of use' intended to be used in the present RollOut-study. This score was calculated as the sum of the answers from a questionnaire with 5 AMISA-specific items. In the best case, this score takes a value of 5, in the worst case a value of 17. The results for the handling score showed that in 82% of cases the score was less or equal 9 points and about 18% greater than 9 points.

To show in a 1-group design (NIS) that this rate can be reduced with the use of pre-rolled TachoSil® significantly to 9%- points ( $\alpha$ = 0.05, power = 80%, two-tailed one group Chi²- test) it takes a minimum of 122 patients without any drop-out (see Table 2 below). To investigate this hypothesis in 3 fields of surgery (gynecology, urology and visceral surgery) independently, a total of 366 patients is needed. Since it is expected to improve the power from 80% up to 90% a minimum of 155 patients in each field and a total up to 465 should be included into the Study.

Test significance level, $\alpha$	0.050	0,050
1 or 2 sided test?	2	2
Null hypothesis proportion, $\pi_0$	0.180	0,180
Alternative proportion, $\pi_A$	0.090	0,090
Power (%)	80	90
N	122	155

Table 2: Comparison of a portion  $\pi_A$  against a fixed portion  $\pi_0$  (asymptotic Chi-test); determined with the program N-Query 7.0 according to Dixon et al. (1983)

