### 3 Introduction

TachoSil® consists of a collagen sealant matrix coated with human fibrinogen and human thrombin for use as a local haemostatic and tissue sealing. This fixed combination is applied directly to the wound surface. Upon contact with blood, body fluids, or physiological saline, the components of the coating dissolve and diffuse into the wound surface. Thrombin converts fibrinogen into fibrin, mimicking the final stage of the coagulation cascade, and forming a cross-linked fibrin clot, which holds the collagen matrix tightly to the wound surface providing local haemostasis and tissue sealing. The active side of the coating sealant matrix is marked in yellow.

Extensive experience on the use of TachoSil® in open invasive surgery and its relevant results in respect to reduction of time to hemostasis, change in length of hospital stay and decrease in postoperative complications encouraged surgeons to apply TachoSil® in minimal invasive (laparoscopic) surgery as well. As laparoscopic techniques require the application of TachoSil® through a trocar, surgeons started preparing TachoSil® themselves raising the need to develop a pre-rolled form which was approved by the European Medicines Agency's Committee for Medicinal Products for Human Use (CHMP) in September 2014.

No clinical trials using pre-rolled TachoSil have been performed. This real-world observational study is conducted to obtain an overview on the ease of use of pre-rolled TachoSil® in laparoscopic use, especially when performing gynaecological, urological and visceral surgery. Additionally, users' satisfaction with the product will be evaluated to confirm procedural advantages of the pre-rolled form in laparoscopic use.

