#### 4.1.9 Assessment

- Assessment of manageability of TachoSil (1-5)
  - o Frequencies
  - o Median / Mean

- Assessment of satisfaction with TachoSil (1-5)
  - o Frequencies
  - o Median / Mean

•

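### The 18%-versus-9% power calculation in Protocol 11.3 belongs to no endpoint or analysis in the study, so neither its power nor an advantage over planar TachoSil can be claimed

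*Protocol*

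**What the plan says.** Protocol 11.3 reports that no published study with the same ease-of-use measure was found, so it used "the results of an older study with a specific MIS -applicator as a surrogate approach". That study summed five device-specific items into a handling score from 5 (best) to 17 (worst), and "in 82% of cases the score was less or equal 9 points and about 18% greater than 9 points". The protocol then asserts: "This parameter comes very close to the parameter 'ease of use' intended to be used in the present RollOut-study".

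On this basis it plans to show that "this rate can be reduced with the use of pre-rolled TachoSil® significantly to 9%- points", with "power = 80%, two-tailed one group Chi²- test". This gives 122 patients per field and 366 over three fields. A second step raises the size to 155 per field and 465 in total: "Since it is expected to improve the power from 80% up to 90"%. The same section expects the pre-rolled form to be easier to apply than planar TachoSil rolled by the surgeon.

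The primary outcomes (Protocol sections 2, 8 and 11.1) are surgeon ratings of ease of use and satisfaction on scales from 1 (best) to 5 (worst). SAP 4.1.9 lists "Assessment of manageability of TachoSil (1-5") and a matching satisfaction item, each with frequencies and median or mean. SAP 4.2.2 repeats the satisfaction rating in the final documentation. The protocol's summary of statistical methods calls the whole analysis descriptive. SAP 2.1 and SAP 7 rule out hypothesis tests, and SAP 2.1 plans about 120 patients.

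Protocol section 3 says that satisfaction will be evaluated "to confirm procedural advantages of the pre-rolled form in laparoscopic use". SAP 1.8 repeats this.

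**The concern.** A one-group test of a proportion needs a yes/no event and a reference rate for that same event. Here the reference rate comes from one instrument and the data from another, and no rule connects the two. The stated power therefore cannot be attached to the ease-of-use rating. Satisfaction, the other primary rating, has no reference rate at all.

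What is at stake is what the report may conclude. Section 11.3 tells a reader that the study has 80% or 90% power to show a significant improvement and expects better handling than the planar form. Section 3 speaks of confirming advantages. A report written against those statements could claim more than an uncontrolled, descriptive study can support.

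**Working it through.** **1. Reproducing the plan's figures.** Inputs from Protocol 11.3: null proportion p0 = 0.18, alternative pA = 0.09, two-sided alpha 0.05, power 80% or 90%. For the asymptotic one-sample test:

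n = [z(0.975)·√(p0(1−p0)) + z(power)·√(pA(1−pA))]² / (p0−pA)²

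- √(0.18 × 0.82) = 0.3842; √(0.09 × 0.91) = 0.2862; (0.09)² = 0.0081.
- 80%: (1.960 × 0.3842 + 0.842 × 0.2862)² / 0.0081 = 121.94, so 122; × 3 = 366.
- 90%: (1.960 × 0.3842 + 1.282 × 0.2862)² / 0.0081 = 154.80, so 155; × 3 = 465.

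Both match. There is no arithmetic error.

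**2. What the test needs and what the documents supply.**

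- *Event.* The old study has a score above 9 on a sum of five items. This study has a rating from 1 to 5, and neither document says which ratings count as unfavourable.
- *Instrument.* Five items with a worst total of 17 cannot all be 1-5 items, because those would reach 5 × 5 = 25. The response options of the old items are not given.
- *Reference rate.* 18% on the old score; none on the 1-5 scale for ease of use, and none of any kind for satisfaction.
- *Planar comparison.* Protocol 7.2 has no treatment groups, and no handling rate for planar TachoSil is given. The SAP 4.2.2 items that refer to an alternative application concern surgery, ICU and care time, not handling.
- *Test.* The SAP plans none.

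**3. How far the power depends on the missing rate.** Assume, for illustration only, some benchmark p0 on the 1-5 scale and a true rate of half that value. With n = 155 and two-sided alpha 0.05, power = Φ{[(p0/2)·√n − 1.960·√(p0(1−p0))] / √((p0/2)(1−p0/2))}:

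| Assumed p0 | Power at n = 155 |
|---|---|
| 5% | 23% |
| 10% | 56% |
| 15% | 81% |
| 18% | 90% |
| 25% | 98% |

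The documents give no basis for choosing a row, because the 18% belongs to the other scale.

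**4. What the size does support.** For a reported rating proportion p, the normal-approximation 95% half-width is 1.96·√(p(1−p)/n).

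| n | p = 18% (assumed) | p = 50% (assumed) |
|---|---|---|
| 120 (SAP total) | ±6.9 points | ±8.9 points |
| 155 (protocol, per field) | ±6.0 points | ±7.9 points |
| 465 (protocol total) | ±3.5 points | ±4.5 points |

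For example, 1.96 × √(0.18 × 0.82 / 155) = 0.060. These values treat ratings as independent. Up to 20 patients may come from one centre, and positive correlation within a surgeon or site would widen the intervals.

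**The case against.** The strongest defence is that nothing turns on the 18%. The protocol openly calls it a surrogate, the analysis is descriptive, and the five-level frequencies will be reported. The stated objectives already speak of describing ease of use and satisfaction. Most of this stands, and it limits the harm. It does not give the power statement a referent, and 11.3 still says that the study is sized to show a significant reduction.

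Three stronger readings are tempting, and the documents do not support them.

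- A reader might infer that a cut-off could be picked after the ratings are seen so that the benchmark appears beaten. The SAP plans no dichotomy and no comparison with 18%, and full frequencies let anyone apply any cut.
- A reader might rescale the old cut to the new scale: 1 + 4 × (9−5)/(17−5) = 2.33, and so call ratings of 3 to 5 the equivalent event. That assumes a linear link between a five-item sum and a single rating. The result also falls between two categories, and the old items' response options are not given.
- A reader might state that the 18% does not come from planar TachoSil. The documents do not say what the applicator delivered; they support only that relevance to the planar form is not shown.

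It is also fair to say that the wording about confirming advantages concerns satisfaction in general, and that SAP 4.1.8 and 4.2.2 collect surgeons' views on preference and advantages. Those views can be described. Without a comparison group they cannot confirm a handling advantage over planar TachoSil.

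Finally, the protocol reviewed carries the date 20 August 2015, while the SAP cites a version of 22 February 2016. Whether 11.3 changed between them cannot be checked here.

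**Conclusion.** The point holds as a mismatch between the sample-size rationale and the study's endpoints and analysis. The figures 122, 155, 366 and 465 are correctly computed, but for an event that this study neither defines nor tests. The 80% and 90% power statements should not be relied on. The study cannot show that the pre-rolled form is easier to use than the planar form, nor confirm a handling advantage over it. It can describe the ratings, with the precision given above under assumed proportions of 18% and 50% and independent observations. Because the planned analysis is already descriptive, the consequence is confined to what is claimed; no planned estimate is wrong.

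**What to change.** - In Protocol 11.3, remove the claim to show a significant reduction from 18% to 9%, the 80% and 90% power statements, and better handling than the planar form as something the study can show.
- Justify the size instead by the confidence-interval width for the reported rating proportions, using the table above. Say whether it applies per field or overall, and note that clustering by surgeon or site is ignored. Use the same rationale for the SAP's figure of about 120.
- State that the 18% will not be used as a comparator for the 1-5 ratings.
- In Protocol section 3 and SAP 1.8, change the verb from confirming to describing.
- Keep the full rating distributions already planned in SAP 4.1.9 and 4.2.2. If any dichotomy is to be reported, for ease of use or for satisfaction, fix its cut in the SAP before database lock and claim no equivalence to the old score.

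The cost is protocol and SAP wording only, with no new data. The drawback is that the stated aim becomes more modest.

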#### 12 Reports

A Non-Interventional Study Report based on the results obtained will be prepared and submitted to Global Medical Affairs for distribution. The Final Study Report should be available within one year from database lock.

#### 13 Publications

Takeda aims to have the results of this study published.

Takeda has the right to use the data and results for regulatory purposes and for internal presentation within the company and to partners.

## 14 Archiving of Study Documentation

During the course of the study the Site Responsible must as a minimum file the essential documents (Section 5.4), the protocol, any amendments, the list of participating patients, the written informed consents, the CRFs and the progress reports in the Study Site File. After final database lock the Site Responsible must as a minimum store the list of participating patients and the signed Informed Consent Forms on site for 10 years. The Site Responsible should store additional study documentation for a longer period of time as required by any local regulations and/or hospital requirement.

